Randomized controlled trial of gabapentin vs placebo for postoperative pain after sacrospinous ligament fixation for pelvic organ prolapse

NCT number: NCT03123861

Document Date: 03-08-17

Randomized controlled trial of gabapentin versus placebo for postoperative pain after sacrospinous ligament fixation for pelvic organ prolapse

Principal Investigator: [name], University of North Carolina at Chapel Hill

BACKGROUND / RATIONALE

Pelvic organ prolapse (POP), the herniation of the bladder, uterus, or rectum, into and often beyond, the vaginal opening, affects 40% of postmenopausal women, and significantly impairs quality of life.(1) POP is often managed surgically, and currently, one in every eight women will undergo POP surgery during her lifetime.(2)

A commonly performed procedure for POP is a sacrospinous ligament fixation (SSLF), which is a vaginal surgery that involves suspending the vaginal apex to the sacrospinous ligament suspension with sutures. Beyond routine postoperative pain, a SSLF may result in significant gluteal pain as a result of the vaginal sutures affecting/impinging on the sacral nerve roots.(3) Unfortunately, postoperative gluteal pain is not uncommon with 12% of patients reporting significant gluteal pain and 4% having persistent pain 6 weeks after surgery.(4)

In this study, we aim to compare the impact of gabapentin versus placebo on postoperative pain after SSLF. Our rationale is that studies have shown that preoperative gabapentin, a non-opioid analgesic, resulted in a lower narcotic use postoperatively.(5) Decreasing use of standard of care postoperative narcotic pain medications would also decrease adverse events due to narcotics such as nausea, vomiting and constipation, and potentially decrease the long-term risk of opioid dependence. (6, 7) As an additional benefit, a careful assessment of actual opioid will help to inform best practices for prescribing, as it is possible that we are overprescribing narcotic medications for this type of surgery.(6, 8, 9) We propose to evaluate a longer two-week course of gabapentin because we currently use gabapentin to treat neuropathic pain after SSLF; thus, gabapentin may help to address overall pain as well as neuropathic gluteal pain that can occur after SSLF. Furthermore, gabapentin is a relatively safe medication with the primary adverse events being dizziness and sedation.

Given the risk of overall postoperative pain and neuropathic gluteal pain after a SSLF for POP and the evidence that perioperative gabapentin may decrease acute pain and neuropathic pain, we propose a novel randomized trial to compare perioperative gabapentin versus placebo on postoperative pain after a vaginal SSLF surgery.

STUDY AIMS

Primary aim: To assess the impact of gabapentin versus placebo on postoperative pain on postoperative day (POD) #7 after a vaginal sacrospinous ligament suspension for apical pelvic organ prolapse.

We hypothesize that a one week course of post-operative gabapentin will decrease overall post-operative pain on POD #7 as compared to placebo.

Secondary aims:

- To assess the impact of gabapentin versus placebo on gluteal postoperative pain on POD#7.
We hypothesize that a one-week course of gabapentin will decrease overall gluteal pain as compared to placebo on POD#7.
- To compare narcotic use during the first two weeks between the gabapentin and the placebo group.
We hypothesize that there will be lower narcotic use in the gabapentin compared to placebo group

STUDY DESIGN & METHODS

This study is a double-blinded randomized controlled trial comparing the impact of 2 weeks of gabapentin vs placebo on post-operative pain.

Study Population

Inclusion criteria:

- Women age 18+
- English-speaking
- Planning to undergo a vaginal SSLF

Exclusion criteria:

- Pregnant or planning to become pregnant during study participation
- Prior or concurrent vaginal mesh surgery for POP (midurethral sling is not an exclusion)
- Planning a concurrent TVH, colpocleisis (total vaginectomy or LeFort colpocleisis), mesh excision, anal sphincteroplasty, fistula repair, or urethral diverticulectomy
- Cognitive impairment (indicated by a score of 0-2 on Mini-Cog)
- Currently taking gabapentin or pregabalin (Lyrica) or previous intolerance to gabapentin or pregabalin
- Daily use of narcotics for \geq 2 months
- Acute or chronic renal failure based on past medical history (PMH) or glomerular filtration rate (GFR) < 30ml/min (see meds info below)
- Severe uncontrolled depression or bipolar disease based on PMH
- Fall risk if history of fall in last year or current use of cane/walker
- Joint procedure with other service (ie colorectal surgery/gyn onc)

Intervention

Participants undergoing SSLF will be randomized to receive either 2 weeks of post-op gabapentin or placebo, starting with 300mg qhs for the first 3 days post-op, then on day 4 patients will dose escalate to 300mg bid for 11 additional days for a total of 2 weeks.

- UNC IDS will provide active and placebo capsules (300mg dose), 1 x 3d postop (subtotal 3), 2 x 11d postop (subtotal 22) = 25 total
- We will use NIH Common Terminology of Criteria for Adverse Events version 4.0 (CTCAE) criteria (15)
- Specific AEs to assess:
 - Dizziness ~ 15%
 - Sedation/somnolence ~ 15%
 - Nystagmus ~ 8% (involuntary movements of the eyeballs)
 - Ataxia ~ 3% (lack of coordination of muscle movements)

Patient incentives

- 6 wk visit - \$50

Data and Safety Management

Study data will be entered into and stored in a secure REDCap database hosted by UNC-CH.

Adverse events will be monitored and assessed using the NIH Common Terminology of Criteria for Adverse Events version 4.0 (CTCAE) criteria, which grades each adverse events from Grade 1 (mild), Grade 2 (moderate), Grade 3 (severe), Grade 4 (life threatening), Grade 5 (death related to AE). (15)

- The PI will be responsible for assessing each AE in terms of whether the AE is expected and/or attributable to the study drug along with the severity of the AE using the CTCAE ratings

- Serious AEs will be reported to the IRB per IRB UPIRSO guidelines
- Specific AEs to assess:
 - Dizziness ~ 15%
 - Sedation/somnolence ~ 15%
 - Nystagmus ~ 8% (involuntary movements of the eyeballs)
 - Ataxia ~ 3% (lack of coordination of muscle movements)

For example, dizziness is rated/described below in the NCI CTCAE(10) Table.

| Nervous system disorders | | | | | |
|--|--|---|--|---|---|
| Adverse Event | Grade | | | | |
| | 1 | 2 | 3 | 4 | 5 |
| Dizziness | Mild unsteadiness or sensation of movement | Moderate unsteadiness or sensation of movement; limiting instrumental ADL | Severe unsteadiness or sensation of movement; limiting self care ADL | - | - |
| Definition: A disorder characterized by a disturbing sensation of lightheadedness, unsteadiness, giddiness, spinning or rocking. | | | | | |

Schedule of Assessments (see Table 1.)

Baseline visit:

Interested patients will be consented and if eligible, baselined at their surgical consult visit or before their pre-op appointment. Participants who have absolute or relative contraindications to gabapentin will be excluded from participation in the study through inclusion/exclusion criteria. This visit may occur up to 3 months before their surgery. Participants will be screened for cognitive impairment by the Mini-Cognitive Assessment, and those who score 2 or less will be considered screen failures. Participants will also complete a standardized and validated symptom bother (PFIQ-sf7) and QoL questionnaires (PFDI-sf20), as well as the standardized and validated PROMIS pain interference, pain intensity, and global mental and physical health questionnaires.

Source data collected as part of routine clinical care may be used to complete CRFs as long as the window between prior data collection and the baseline visit does not exceed 18 months. This includes previously performed POP-Q exams as well as previously collected questionnaires.

- Informed consent
- Inclusion/Exclusion Form
- Baseline form (Demographics, Medical & Surgical History, pain/analgesic med use, POP-Q exam record)
- Mini-Cognitive Assessment
- PFIQ-sf7, PFDI-sf20, PROMIS questionnaires

Randomization:

The randomization table will be given to IDS who will implement randomization for the study and provide the study drug that will be given to patients before their surgery. Randomization will be done by site – Hillsborough and Rex, in a 1:1 ratio and in blocks of 4.

Surgery:

Surgical data will be collected on a Surgical Procedures Form and include items listed below.

- American Society of Anesthesiologists (ASA) grade
- Concomitant procedures performed
- Estimated blood loss (EBL)
- Intraoperative complications
- Voiding trial results

Follow-Up Procedures:

- Daily for 2 weeks after discharge: Patients will complete a Study Drug-Pain Med Count Form and Surgical Pain Scale ratings every day for the first 2 weeks after discharge.
- 2-3 days after discharge: We will call patients 2-3 days after discharge to assess for any AEs and remind pts to dose escalate. We will use the NIH Common Terminology of Criteria for Adverse Events version 4.0 (CTCAE) to determine AE severity/grade.
- Week 1 and Week 2 calls: At Week 1 and Week 2 we will call patients to administer the PROMIS questionnaires. We will also remind patients to complete the Study Drug-Pain Med Count Form and Surgical Pain Scale, and will review any potential AEs.
- Week 3, 4, 5: Patients will complete the PROMIS questionnaires, as well as a Pain Med Count Form and Surgical Pain Scale at the end of week 3, 4, and 5 post-operatively.

Week 6 Visit:

Patients will return to clinic for a postoperative visit around week 6, in which all of the assessments listed in the table below will be performed. Patients will again complete the symptom bother (PFIQ-sf7) and QoL questionnaires (PFDI-sf20), as well as the PROMIS pain interference, pain intensity, and global mental and physical health questionnaires. In addition, we will assess for any AEs or post-operative complications that may have occurred since discharge, as well as current pain/analgesic med use.

- Week 6 form (pain/analgesic med use, post-op complications)
- PFIQ-SF7, PFDI-SF20, PROMIS questionnaires
- Surgical Pain Scale

Table 1. Schedule of Assessments

| Schedule of Assessments | # ?s | Baseline | 2-3 day post-op call | Daily for 2 wks post-op (completed at home) | Wk 1 call | Wk 2 call | Every wk Wk 3-5 (completed at home) | 6 Wk visit |
|--|------|----------|----------------------|---|-----------|-----------|-------------------------------------|------------|
| PFDI-20 | 20 | X | | | | | | X |
| PFIQ-7 | 7 | X | | | | | | X |
| PROMIS pain interference/intensity | 7 | X | | | X | X | X | X |
| PROMIS depression/anxiety short forms | 8 | X | | | | | | X |
| PROMIS global mental/physical health | 4 | X | | | X | X | X | X |
| Medical/Surgical history | | X | | | | | | |
| Pain medications assessment | | X | | | | | X | X |
| Study Drug-Pain Med Count Form | | | | X | X | X | | |
| Surgical pain scale (SPS) + gluteal pain | 6 | | | X | X | X | X | X |
| Adverse events assessment | | | X | | X | X | | X |
| Total # of questions at each visit | | 46 | | 6 | 18 | 18 | 18 | 52 |

Outcome measures

Primary Outcome

Overall post-operative pain will be measured by item 2 of the surgical pain scale (SPS) on post-op day 7. This item measures the average pain felt during normal activity in the last 24 hours on a scale of 1-10.

(SPS validated by OPTIMAL study and in older women; OPTIMAL was a multicenter NIH sponsored Pelvic Floor Disorders Network study comparing SSLF to uterosacral ligament suspension surgery for POP).(11, 12)

Secondary outcomes:

1. Gluteal pain on post-op day 7 will be measured by a numeric rating scale like that used in the SPS (0-10)
2. Other pain scale items such as SPS pain at rest, pain w/normal activity (primary outcome), unpleasantness of worst pain sensation, gluteal pain at rest and gluteal pain w/normal activity on POD#7
3. Daily Narcotic pain medication use for 2 weeks post-op and then through week 6 post-op

DATA ANALYSIS

Sample size

OPTIMAL study found that SPS score for pain with normal activity

- Wk 2 = mean 2.9 (2.6 SD) median 2 (1-4 IQR) range: 0-10
- Pain is likely to be higher at Wk 1
- 17 per group to detect 2.5 difference in SPS, SD 2.6 with alpha 5%, power 80%
- **If 20% drop out, need 19 per group so 38 total at min**

Statistical Analysis Plan

- Bivariate analyses to compare our two cohorts: Student's t-test, chi-square/Fisher's exact and Mann-Whitney U for continuous variables, categorical variables and ordinal/skewed data respectively.

Primary outcome

- We will compare pain with normal activity scores on POD#7 using Student's t-test or Mann-Whitney U as appropriate

Secondary outcomes

- We will use Student's t-test or Mann-Whitney U as appropriate to compare gluteal pain scores on POD#7
- We will compare total narcotic use in average morphine milliequivalents per day during the first two weeks using Student's t-test or Mann-Whitney U as appropriate
 - Convert different narcotics into morphine equivalents and add up total narcotic use as needed
 - Compare with t-test if parametric vs Mann-Whitney U if nonparametric
 - Perform a linear regression analysis and adjust for baseline pain medication usage in order to account for the fact that baseline pain medication usage may impact postoperative narcotic use. We can also adjust for postoperative non-narcotic pain medication.

References

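### The targeted adverse-event list omits nausea, vomiting, constipation and falls, leaving them to general enquiry, and the SAP specifies no adverse-event summary by arm

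*Combined protocol and SAP*

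**What the plan says.** The BACKGROUND / RATIONALE section argues that lower use of postoperative narcotics "would also decrease adverse events due to narcotics such as nausea, vomiting and constipation". The same section gives dizziness and sedation as gabapentin's main adverse effects.

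The exclusion criteria include "Fall risk if history of fall in last year or current use of cane/walker".

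The list headed "Specific AEs to assess" appears under Intervention and again under Data and Safety Management. Both times it has the same four terms with approximate rates: dizziness 15%, sedation/somnolence 15%, nystagmus 8% and ataxia 3%.

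Collection is not limited to those four. Data and Safety Management applies CTCAE version 4.0 grading to adverse events in general. Follow-Up Procedures states: "We will call patients 2-3 days after discharge to assess for any AEs". The week 1 and week 2 calls also review possible adverse events, and the week 6 visit covers adverse events and postoperative complications since discharge. Table 1 marks an adverse-event assessment at these four contacts.

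Narcotic use over the first two weeks is a secondary aim, and the Statistical Analysis Plan gives it an analysis. No adverse event appears under Outcome measures. The Statistical Analysis Plan mentions none either; it has only a general line on bivariate tests between the two groups.

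**The concern.** The plan creates two tiers of collection. Four terms are singled out for assessment, and everything else depends on a general question whose wording the documents do not give. Nausea, vomiting and constipation, the events by which patients would feel the benefit of narcotic sparing, fall in the second tier. So do falls, although three of the four named terms (dizziness, sedation, ataxia) could plausibly lead to one and women at known risk of falling are excluded.

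Events asked about by name are usually recorded more completely than events left to a general question, particularly when, like nausea and constipation, they are common and expected after surgery. The trial would then describe the listed gabapentin effects in more detail than the narcotic effects. Narcotic consumption does not fill the gap: it measures the intermediate step, not whether patients felt better for it. Symptoms not asked about at the time cannot be reliably recovered later. Because no summary by arm is planned, it is also unspecified how any of these events, listed or not, would be reported.

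**Working it through.** **1. Where each term appears**

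| Term | Rationale | Exclusion criteria | Targeted list (both places) | Outcome measures | SAP |
|---|---|---|---|---|---|
| Dizziness, sedation | Yes | No | Yes | No | No |
| Nystagmus, ataxia | No | No | Yes | No | No |
| Nausea, vomiting, constipation | Yes | No | No | No | No |
| Falls | No | Yes | No | No | No |

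All of them can be recorded through the general enquiry at four contacts: the 2-3 day call, the week 1 and week 2 calls, and the week 6 visit. The omission is from the targeted list, not from adverse-event collection as a whole.

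**2. What incomplete capture does (assumed figures)**

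The documents give no rates for narcotic adverse events and no capture fractions. Assume true rates of 40% on placebo and 25% on gabapentin. Observed rate = true rate × capture, with the same capture in both arms.

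| Assumed capture | Placebo | Gabapentin | Difference | Ratio |
|---|---|---|---|---|
| 95% | 0.40 × 0.95 = 38.0% | 0.25 × 0.95 = 23.75% | 14.25 points | 1.6 |
| 50% | 20.0% | 12.5% | 7.5 points | 1.6 |
| 30% | 12.0% | 7.5% | 4.5 points | 1.6 |

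The absolute difference shrinks from the true 15 points. The direction and the ratio do not change.

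**3. What the trial's size allows**

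The Sample size section gives 17 per group for a difference of 2.5, SD 2.6, alpha 5% and power 80%. Check (normal approximation, two-sided): 2 × (1.960 + 0.842)² × 2.6² / 2.5² = 16.98, so 17. That figure reproduces. The planned enrolment is 19 per group. How 19 was derived from 17 is a separate matter; it is used here only as the planned number.

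Chance of at least one case in an arm of 19, at the plan's own listed rates, 1 − (1 − p)¹⁹:

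- p = 15%: 1 − 0.85¹⁹ = 95%
- p = 8%: 1 − 0.92¹⁹ = 79%
- p = 3%: 1 − 0.97¹⁹ = 44%

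Power of a two-sided Fisher's exact test at 5% with 19 per arm, summing the binomial probabilities of all tables with p ≤ 0.05 (all rates assumed):

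| Assumed rates | Power |
|---|---|
| 30% v 15% | 11% |
| 40% v 25% | 10% |
| 40% v 20% | 18% |
| 50% v 25% | 27% |
| 60% v 30% | 37% |
| Falls, 5% v 1% | under 1% |

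Precision is similarly limited. With no falls among 19 women, the exact two-sided 95% upper limit is 1 − 0.025^(1/19) = 17.6%.

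Naming the extra terms therefore gives fuller, more even description. It does not give a usable test, and it changes no sample size.

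**The case against.** The strongest reply is that the list does a defensible job. It sits beside the drug description and the investigator's duty to judge whether an event is expected and attributable to study drug, so it naturally names study-drug effects. Staff enquire about adverse events in general at four contacts, and the week 6 form has an item for postoperative complications. The file contains no call script, so it is not known that the omitted events would be recorded only when a patient volunteers them. This stands, and it limits the point to likely completeness of capture.

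A reader might go further and infer that the safety comparison is one-sided or tilted against gabapentin. The documents do not support that. The trial is double-blind and both arms have the same contacts, so under-capture of a given event should be similar in each arm, as the constant ratio of 1.6 illustrates. Unevenness arises only when one type of event is weighed against another, and the plan proposes no such weighing. Nor does it define an adverse-event comparison at all. That absence is the more basic gap.

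A reader might also infer that the trial cannot bear on its own benefit claim. That too is more than the documents support. The reduction in narcotic adverse events is background rationale, not an aim or hypothesis; the step the trial does examine, narcotic use, is measured daily and analysed; and general adverse-event reports can still contribute, if less completely.

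It is fair to add that four more questions would not let a trial of this size settle the matter. That is true, and the recommendation does not claim otherwise.

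**Conclusion.** The point holds as a modest one. The targeted list omits nausea, vomiting, constipation and falls, although the protocol itself gives reasons to be interested in them, and the SAP specifies no adverse-event summary by arm. The likely effect is less complete capture of these events in both arms, and so smaller absolute differences. The size is unknown: the fall from 15 points to between 4.5 and 7.5 rests wholly on assumed event rates and assumed capture of 30% to 50%. The conclusion also assumes that named questions capture more than general ones and that capture does not differ by arm.

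The primary outcome, the secondary outcomes and the sample size are unaffected. This is a cheap improvement, worth making before enrolment because the data cannot be reliably collected afterwards.

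**What to change.** 1. Add nausea, vomiting, constipation and any fall since the last contact to the targeted list, under both Intervention and Data and Safety Management.
2. Ask all eight terms by name, in the same words in both arms, at the 2-3 day call, the week 1 and week 2 calls and the week 6 visit, and grade them by CTCAE. Keep the general adverse-event question as well.
3. Add a line to the Statistical Analysis Plan: for each of the eight terms, the number and percentage of patients affected by arm with exact 95% confidence intervals; other adverse events tabulated by arm; all of it descriptive.
4. State that the trial is not sized to test whether narcotic adverse events are reduced.

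The cost is a minor amendment to the protocol and forms, about a minute more per contact, and more low-grade events to log. No visit is added, and treatment, eligibility and sample size do not change.

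### Nystagmus is named for assessment, but no scheduled contact can observe it while patients are on study drug, so it is likely to be under-counted

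*Combined protocol and SAP*

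**What the plan says.** Under Intervention, and again under Data and Safety Management, the protocol lists four adverse events for specific attention: dizziness, sedation or somnolence, nystagmus and ataxia. The last two carry an expected rate and a plain-language gloss: "Nystagmus ~ 8% (involuntary movements of the eyeballs" and "Ataxia ~ 3% (lack of coordination of muscle movements".

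The course is two weeks. After three days at the starting schedule, "on day 4 patients will dose escalate to 300mg bid for 11 additional days for a total of 2 weeks".

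Adverse events are collected at four contacts:

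- Early call (Follow-Up Procedures): "We will call patients 2-3 days after discharge to assess for any AEs and remind pts to dose escalate".
- Week 1 and week 2 calls: "At Week 1 and Week 2 we will call patients to administer the PROMIS questionnaires". The same entry adds that staff will remind patients about their forms "and will review any potential AEs".
- Week 6 Visit: "Patients will return to clinic for a postoperative visit around week 6". Adverse events and complications since discharge are asked about there.

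The adverse event row of Table 1 marks the same four contacts and no others. The forms completed at home, daily for two weeks and then at weeks 3 to 5, carry no adverse event item. No examination of eye movements, gait or coordination is described at any contact, and no set of symptom questions is described for the calls.

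**The concern.** What is to be assessed does not match how it is to be assessed. Dizziness and sedation are symptoms, and a telephone call can collect them. Nystagmus, as the protocol glosses it, is an eye movement that an observer sees. A patient may not notice it, and a caller cannot see it. By the time a clinician is scheduled to see the patient after discharge, nobody should still be taking study drug, and the visit can only ask for recall.

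At stake is what an empty nystagmus line in the safety record would mean. Under this schedule it could mean that the sign did not occur or that nobody was in a position to see it, and the record would not tell the two apart. The placebo arm does not help, since cases that cannot be observed are missed in both arms.

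Ataxia raises a smaller version of the problem. A patient can describe poor coordination by telephone. But the one grading table shown, for dizziness, defines grades 1 to 3 by unsteadiness. Unless coordination is asked about separately, such a report may be coded as dizziness.

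**Working it through.** **1. Length of the course.** Inputs are from Intervention. Days: 3 + 11 = 14. Capsules: 3 × 1 + 11 × 2 = 3 + 22 = 25. This reproduces the plan's own count, "1 x 3d postop (subtotal 3), 2 x 11d postop (subtotal 22) = 25 total".

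**2. Gap to the clinic visit.** Taking week 6 as day 6 × 7 = 42, the gap is 42 − 14 = 28 days, about four weeks.

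**3. Contacts set against exposure** (Follow-Up Procedures, Week 6 Visit, Table 1).

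| Contact | Mode | Relation to dosing | Eyes visible? |
|---|---|---|---|
| 2-3 days after discharge | Telephone | During | No |
| Week 1 | Telephone | During | No |
| Week 2 | Telephone | At about the end | No |
| Week 6 | Clinic | About 28 days after | Yes, but off drug |

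No row has both exposure and a view of the patient.

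**4. Expected cases on gabapentin.** Inputs: 19 per group (the planned minimum in Sample size, taken as stated) and the protocol's 8% and 3%. This assumes that those rates apply to this course and that all 19 take the drug and are followed.

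- Nystagmus: 19 × 0.08 = 1.52. Chance of at least one case: 1 − 0.92^19 = 1 − 0.205 = 79.5%.
- Ataxia: 19 × 0.03 = 0.57. Chance of at least one case: 1 − 0.97^19 = 1 − 0.561 = 43.9%.

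**5. Effect of incomplete detection.** The documents give no share of true cases that a call would record, so that share, s, is an assumption shown over a range. Expected recorded cases are 19 × p × s. The chance of recording at least one is 1 − (1 − p × s)^19.

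| s | Nystagmus: expected | At least one | Ataxia: expected | At least one |
|---|---|---|---|---|
| 1 | 1.52 | 79.5% | 0.57 | 43.9% |
| 0.75 | 1.14 | 69% | 0.43 | 35% |
| 0.5 | 0.76 | 54% | 0.28 | 25% |
| 0.25 | 0.38 | 32% | 0.14 | 13% |
| 0.1 | 0.15 | 14% | 0.06 | 5.5% |

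The lower values of s are more plausible for nystagmus than for ataxia, but nothing in the documents fixes either.

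**6. What a zero could show with perfect detection.** For 0 of 19, the exact two-sided 95% upper limit is 1 − 0.025^(1/19) = 17.6%, above both 8% and 3%.

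**The case against.** Several objections have force.

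- **These are not outcomes.** Outcome measures covers pain and narcotic use only. Nystagmus and ataxia are adverse events named for monitoring, with expected rates against which the investigator can judge whether an event is expected. This stands.
- **No rate is planned.** A reader might infer that the trial will report a zero as a measured incidence and so give false reassurance about the drug. The documents do not support that. The Statistical Analysis Plan contains no adverse event rate, table or between-arm comparison. With an upper limit of 17.6% for 0 of 19, a zero would reassure little even if every patient were examined. This stands.
- **The shortfall is not shown.** The documents do not say how the 8% and 3% were ascertained. If they came from patient reports, telephone collection could be comparable. This stands as to size.
- **Ataxia can be reported.** A reader might group the two signs together as equally invisible. The protocol's own gloss describes something a patient or household member can notice, so the point rests mainly on nystagmus.
- **Prompts may already exist.** The public document holds no call script, and callers may well ask about the four named events. That is possible, and it would remove part of the gap. But the text describes only a general review, and no prompt lets a caller see the eyes.
- **Other opportunities.** Ward staff may notice a sign before discharge, and the week 6 visit asks back to discharge. The first is not a scheduled assessment and the second depends on recall.

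What survives is narrower: for nystagmus, the method of ascertainment does not fit the event named.

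**Conclusion.** The mismatch is real and follows directly from the schedule: every assessment during or at the end of the 14-day course is a telephone call, and the only postoperative clinic visit comes about 28 days later. Nystagmus is therefore likely to be under-counted. That is an inference from the kind of sign it is, and its size cannot be computed from these documents. Ataxia is affected less, mainly through possible coding as dizziness.

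The consequence is small. With 19 on gabapentin and the protocol's rates, between one and two nystagmus cases and at most about one ataxia case would be expected, so the trial could not characterise either event under any schedule. This is a low-severity improvement to the safety record. It has no bearing on the pain or narcotic-use comparisons, and the schedule is not evidence that the safety conclusions will be wrong.

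**What to change.** On each of the three existing calls, ask a short fixed set of questions that a patient can answer, worded identically in both arms. Examples are jumping, double or blurred vision, and trouble with coordination or walking, the latter asked separately from dizziness. Record the answers as reported symptoms, alongside the four named events and not in place of them.

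Add a statement to Data and Safety Management that nystagmus was not examined on treatment, and that its absence will not be reported or interpreted as a measured zero incidence.

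The cost is a few lines on the call script and one sentence in the protocol, with no extra visit or staff. The downside is that prompted questions raise non-specific reports in both arms; the blinded placebo arm helps to interpret them. If a script with such questions already exists, citing it in the protocol and adding the statement is enough.

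### Baseline pain scores and analgesic use, including the only baseline covariate in the SAP, may be up to 21 months old at surgery, with no rule requiring an update

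*Combined protocol and SAP*

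**What the plan says.** Three statements in the protocol's Baseline visit section, under Schedule of Assessments, set the rule.

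- Timing of the visit: "This visit may occur up to 3 months before their surgery".
- Reuse of earlier data: "Source data collected as part of routine clinical care may be used to complete CRFs". An age limit on this reuse is attached, worded "as long as the window between prior data collection and the baseline visit does not exceed 18 months".
- Examples of what may be reused: "This includes previously performed POP-Q exams as well as previously collected questionnaires".

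The same section says that participants complete questionnaires at this visit, "as well as the standardized and validated PROMIS pain interference, pain intensity, and global mental and physical health questionnaires". It also lists the contents of one study form: "Baseline form (Demographics, Medical & Surgical History, pain/analgesic med use, POP-Q exam record". No sentence exempts the pain questionnaires or analgesic use from reuse, or requires either to be updated before surgery.

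Table 1 marks PROMIS pain interference/intensity and a pain medications assessment at baseline. The Surgical Pain Scale has no baseline mark, so PROMIS pain is the only pain scale scheduled before the operation.

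The Statistical Analysis Plan compares the primary outcome, pain with normal activity on day 7, by an unadjusted two-group test. For narcotic use, a secondary outcome, it adds a model: "Perform a linear regression analysis and adjust for baseline pain medication usage". Its stated reason is that such usage may affect narcotic use after surgery.

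**The concern.** Pain and analgesic use can change over many months. POP-Q stage and surgical history are slower to change, yet one 18-month allowance covers all of them.

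Two things are at stake. First, the narcotic-use regression is meant to allow for what participants were taking going into surgery. A record taken more than a year and a half earlier need not measure that, so the adjustment may not do the job the SAP gives it. Second, in a trial planned at 19 per group, chance imbalance in pain before surgery is plausible, and baseline PROMIS pain is the scheduled measure that would show it. If some scores are current and others are old, the baseline table is harder to read. Any comparison with the PROMIS pain scores at weeks 1 to 6 would also start from mixed time points.

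**Working it through.** **Step 1. Maximum age.** The documents state no total, so there is no figure of the plan's own to reproduce. Earlier data may be 18 months older than the baseline visit, and that visit may be 3 months before surgery: 18 + 3 = 21 months.

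**Step 2. What the allowance reaches, and where it is used.**

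| Item | Covered by the allowance? | Used in a stated analysis? |
|---|---|---|
| POP-Q | Yes, named | No |
| PROMIS pain | Yes, as a questionnaire | No stated model |
| Analgesic use | Not named; covered by the general CRF wording because it is on the Baseline form | Yes, covariate in the narcotic-use regression |

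POP-Q, which is named as reusable, sits on the same Baseline form as analgesic use. The only other covariate mentioned is optional ("We can also adjust for postoperative non-narcotic pain medication"). It is measured after surgery, so the allowance does not touch it.

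**Step 3. Effect on the narcotic-use regression.** The documents give no correlations, so these are assumptions. Let r be the correlation of current analgesic use with the outcome. Let ρ be the correlation of the old record with current use. Assume the old record relates to the outcome only through current use, and that every participant's record is old. Then

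residual-variance factor = 1 − (r × ρ)²

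| r | ρ = 1 (current record) | ρ = 0.8 | ρ = 0.6 | ρ = 0.4 |
|---|---|---|---|---|
| 0.3 | 0.91 | 0.94 | 0.97 | 0.99 |
| 0.5 | 0.75 | 0.84 | 0.91 | 0.96 |
| 0.7 | 0.51 | 0.69 | 0.82 | 0.92 |

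For example, with r = 0.5 and ρ = 0.6: 1 − (0.30)² = 0.91, against 1 − (0.5)² = 0.75 with a current record.

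The share of the variance reduction that is lost is 1 − ρ², whatever r is. At ρ = 0.6 it is 1 − 0.36 = 0.64; at 0.8 it is 0.36; at 0.4 it is 0.84.

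The standard error of the adjusted treatment difference scales with the square root of the factor. At ρ = 0.6, relative to a current record:

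- r = 0.3: √(0.968/0.91) = 1.03
- r = 0.5: √(0.91/0.75) = 1.10
- r = 0.7: √(0.824/0.51) = 1.27

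**Step 4. Bias.** Allocation is randomised, and the covariate is recorded before treatment in both arms. Noise in it weakens the correction of chance imbalance and costs precision. It does not by itself bias the treatment comparison.

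**Step 5. Primary analysis.** The day-7 test contains no baseline term, so the age of baseline data does not enter it.

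**The case against.** The strongest reply has four parts.

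- **Analgesic use is not named in the reuse sentence.** This is correct. It comes in through the general wording on CRFs, and the named items are introduced only as inclusions. The plan therefore permits the reuse without expressly providing for it.
- **Current medication information is needed at enrolment anyway.** The exclusion criteria cover current gabapentin or pregabalin and daily narcotic use for 2 months or more. This stands in part. Excluding sustained daily narcotic users also narrows how far baseline narcotic use can vary. However, the criteria do not call for current non-narcotic analgesics or intermittent narcotic use, and they are recorded on a separate form.
- **Participants are said to complete PROMIS at baseline, and reuse is only permissive.** This is true, but the next paragraph allows earlier questionnaires to stand in, and the two are not reconciled. The documents do not say how often routine-care PROMIS pain scores exist, so the number of participants affected is unknown.
- **21 months is a ceiling.** This stands. If only some records are old, the loss is smaller than the table in the working shows.

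A reader might infer more: that the primary outcome loses power because baseline pain, a natural covariate for it, may be stale. The documents do not support that. The planned primary test is unadjusted and PROMIS scores are covariates in no stated model. Any such figure would measure a gain forgone in an analysis that the plan does not contain. Nor can one say that the SAP's covariates in general are out of date, because only one baseline covariate is named.

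**Conclusion.** The point holds in limited form. The plan permits baseline pain scores, and through its general wording the analgesic-use covariate, to be up to 21 months old at surgery, and nothing requires an update. One planned analysis is affected: the regression for narcotic use, whose covariate may then fail its stated purpose. The unadjusted comparison of narcotic use that the SAP also lists is untouched.

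The size rests on assumed correlations and on all records being old. With r from 0.3 to 0.7 and ρ = 0.6, about 64% of the variance reduction from adjustment is lost, and the standard error is about 3% to 27% larger than with current records. The harm is to precision and to the correction and display of chance imbalance. It is not a source of bias and does not weaken the primary analysis. The change is a cheap improvement, worth making before enrolment because a missed contemporaneous baseline cannot be recovered after surgery.

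**What to change.** Restrict the 18-month allowance to the POP-Q exam, demographics, and medical and surgical history. Require PROMIS pain interference and intensity, and the pain/analgesic-use section of the Baseline form, to be completed as current at the study baseline visit. This also settles the tension between completing the questionnaires at the visit and reusing earlier ones. The maximum age of these items at surgery falls from 21 months to 3.

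The cost is a sentence or two in the protocol, and a few minutes for participants whose old records would otherwise have been reused. They already have this visit, so no contact is added. Sample size and the planned tests do not change.
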